5.1 Primary objectives

The primary research question is whether the addition of PCT measurement to NEWS2 scoring can lead to a reduction in intravenous antibiotic initiation in ED patients managed as suspected sepsis, with at least no increase in 28-day mortality compared to NEWS2 scoring alone (in conjunction with local standard care pathways).

5.2 Secondary objectives

To determine if the use of PCT and NEWS2 in the assessment of suspected sepsis is:

- i) cost-effective,
- ii) feasible
- iii) acceptable to patients and their family.

5.3 Primary outcomes measure(s)

The study will use the following as co-primary outcomes:

- Intravenous antimicrobial initiation – binary outcome assessed at 3 hours.
- 28-day mortality – binary outcome.

Final decisions about the primary effectiveness, using these co-primary outcomes will be made based on:

	Reduced antibiotic initiation	Same or more antibiotic initiation
Decreased mortality	Effective	Effective
Equivalent mortality	Effective	Not effective
Increased mortality	Not effective / harmful	Not effective / harmful

5.4 Secondary outcomes measure(s)

Time until initiation of IV antibiotic therapy

Late IV antibiotic initiation – antibiotics commenced after 3 hours

Number of days on IV antibiotics (during admission and total over the first 28 days).

Number of days on any antibiotic (during admission and total over the first 28 days).

Number of days on broad spectrum antibiotics (IV and oral), defined by number of days on an Access group of antibiotics as defined by WHO [AWaRe Classification Database](#) (during admission and total over the first 28 days).

ICU admission – at any point during admission

Length of ICU stay

Length of hospital stay

Adverse antibiotic outcomes

Readmission to hospital within 90 days

Mortality within 90 days (and time until death)

Health utility (EQ-5D/5L) at 28 and 90 days

Health resource usage

Feasibility of implementing PCT testing alongside NEWS2 scoring in EDs

Acceptability of implementing PCT testing alongside NEWS2 scoring in EDs, to patients, carers and clinicians

Planned stratification of all outcomes by COVID-19 diagnosis

6 Trial design and setting

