the control arms of these studies were representative of standard practice in the UK. The report recommended further studies of PCT to guide antibiotic treatment in adults with suspected or confirmed sepsis in ED settings, including research examining (short-term) health-state utility values. A recent patient level meta-analysis of randomised trials assessing the use of procalcitonin guided antibiotic treatment on outcomes for patients with infection and sepsis in intensive care settings suggests that procalcitonin use can significantly reduce mortality and antibiotic treatment duration [28]. A large prospective study of adult medical patients presenting to the ED demonstrated that admission PCT was a strong and independent predictor of 30-day mortality. The use of PCT in addition to qSOFA improved prognostic accuracy [29]. This suggests that PCT may help to improve risk stratification in suspected sepsis if combined with NEWS2.

The objective of this trial is not to prevent patients who require antibiotics from receiving antibiotics. It will assess whether by using NEWS2 and PCT, we can identify patients who require antibiotics within 1 hour whilst providing more time for clinicians to decide if antibiotics are required for patients who are less severely ill. It may therefore lead to less antibiotics and more narrow spectrum antibiotics being prescribed as clinicians may have more time to assess patients before they prescribe antibiotics. The rapid result of the PCT test, especially if it indicates a low or medium risk, may also provide reassurance to patients and families, and reduce anxiety.

5 Trial objectives/endpoints and outcome measures

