11.1 Assessments

Outcome data will be recorded daily by the research nurse for all recruited participants (up to and including Day 28, or until discharge). Patient reported outcome data (health-related quality of life and resource use questionnaires) will be recorded at day 28 and day 90 (with the exception of those recruited within the last 3 months of the study).

Research nurses will review observation and medication charts, and medical notes for all recruited participants to collect the data described in Table 1 below:

Table 1: Outcome data collection

Outcome	Data Source	Type of data	Frequency	By Whom
Antibiotic (Abx) initiation	Observation (Obs) charts/medical notes/drug charts	Time of initiation, Abx type, dose, duration	Admission/Daily	Research Nurse
Abx use (IV and Oral) in-patient	Obs charts/medical notes/drug charts	Abx type, dose, duration	Daily	Research Nurse
Abx use (IV and Oral) post discharge up to 28 days	Obs charts/medical notes/drug charts/patient report/GP record	Abx type, dose, duration	At 28 day	Research Nurse
Adverse events	Obs charts/medical notes	Date, type	Daily	Research Nurse
ICU usage	Medical notes	Date, details of admission to ICU	Daily	Research Nurse
COVID diagnosis	Medical notes	Date, clinical or laboratory confirmed	At 28 day	Research Nurse
Unscheduled readmissions	Medical notes	ICU re-admissions, re-admissions post discharge	Daily	Research Nurse
Mortality	Medical notes	Date, Description	If before Day 28	Research Nurse
Discharge	Medical notes	Date, Description	If before Day 28	Research Nurse
Serious Adverse Drug Reactions (ADRs)	Medical notes	ADR(s)	Daily	Research Nurse
Health utility	Patient reported	-	Day 28 and Day 90	EQ-5D/5L, Patient reported questionnaire, collected by

				telephone or by post
Health-related Quality of Life (EQ-5D/5L)	Patient reported	-	Day 28 and Day 90	Patient reported, collected by telephone, or by post
Resource use	Patient reported	Direct medical costs and resource use	Day 28 and Day 90	Patient reported, collected by telephone, or by post

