Antibiotic usage	No of days on IV antibiotics No of days on all antibiotics No of days on broad spectrum antibiotics	In hospital	Linear regression
Antibiotic adverse outcomes	Anticipated drug reactions include: diarrhoea, C. difficile , acute kidney injury, hearing loss etc.	In hospital	Logistic regression
ICU usage	People admitted to ICU No of days in ICU	In hospital	Logistic regression Linear regression
Readmission to hospital	People with one or more readmissions	After discharge	Logistic regression
Mortality	Time until death	90* days	Cox regression
Health utility	EQ-5D-5L	90* days	Linear regression of transformed outcome measure

* Except for patients recruited during the last 3 months of the study.
Full details of all analyses will be provided in the PRONTO SAP.

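### Section 5.4 counts days on AWaRe Access-group agents as days on broad-spectrum antibiotics, which is probably the wrong group, so this one secondary outcome can understate a spectrum benefit or, for large enough shifts, reverse its sign

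*Protocol*

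**What the plan says.** Protocol section 5.4 includes the secondary outcome "Number of days on broad spectrum antibiotics (IV and oral"), measured during admission and over the first 28 days. It gives the derivation in the same sentence: "defined by number of days on an Access group of antibiotics as defined by WHO", with a link to the "AWaRe Classification Database". No other AWaRe group is named anywhere in the protocol, and the contents of the groups are not listed.

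Table 3 in section 17.1 repeats the measure as "No of days on broad spectrum antibiotics", to be analysed by linear regression, and does not define it again.

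On the expected effect of the intervention, section 4 (Background) says: "It may therefore lead to less antibiotics and more narrow spectrum antibiotics being prescribed".

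Table 1 in section 11.1 records "Abx type, dose, duration" for inpatient antibiotics and for antibiotics after discharge up to day 28.

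**The concern.** The label and the derivation appear to point in opposite directions. The rule in section 5.4 is complete: a day on an Access agent counts, and a day on anything else does not. By the ordinary meaning of the classification, Access is the first-choice, mainly narrower-spectrum tier, and the broader agents that stewardship tries to limit lie mostly in Watch and Reserve. The rule would then leave out most of the days it is meant to capture and count many days it is meant to exclude.

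Spectrum is part of the trial's rationale. The Background cites an 83% rise over three years in intravenous broad-spectrum use in emergency departments, and evidence that unnecessary broad-spectrum exposure may be harmful. In section 5.4 this is the only outcome that measures spectrum. If procalcitonin (PCT) testing shifts prescribing toward narrower agents, the written outcome could record that shift as more broad-spectrum days in the PCT arm.

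This is not detail left for the SAP. The protocol states the derivation itself, so an SAP that used a different one would contradict it.

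**Working it through.** The protocol states no figure for this outcome, so there is none to reproduce. The check applies the rule literally and then asks when the direction of the result would mislead.

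**Step 1: the rule applied to three records**

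| Record | Section 5.4 rule (Access days) | Watch/Reserve days |
|---|---|---|
| 7 days on a Watch agent only | 0 | 7 |
| 7 days on an Access agent only | 7 | 0 |
| 2 days on a Watch agent, then 5 on an Access agent | 5 | 2 |

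**Step 2: inputs for an illustration**

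- From section 16.2: 90% receive antibiotics in the control arm. For the PCT arm, 80% is the reduction that would count as success, and 87.6% is given as the smallest effect detectable with 90% power.
- Assumed, not in the protocol: a mean course of 7 days; 60% of treated control patients start on a Watch/Reserve agent; 30% of those switch to an Access agent after 2 days; the treated share equals the initiation share, so later starts are ignored.
- Let t be the share treated, p the share of treated patients starting on Watch/Reserve, and f the share of Access days that are in truth broad spectrum. Because the list is not reproduced, f is taken from 0 to 1. Non-Access days are assumed broad.

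A Watch/Reserve starter has 0.7 × 7 + 0.3 × 2 = 5.5 Watch/Reserve days and 7 − 5.5 = 1.5 Access days. An Access starter has 7 Access days. Per randomised patient:

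- Outcome as written: A = t × (7 − 5.5p)
- Watch/Reserve days: W = t × 5.5p
- Intended outcome: W + f × A

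Control arm: A = 0.9 × (7 − 3.3) = 3.33 and W = 0.9 × 3.3 = 2.97.

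**Step 3: difference, PCT minus control, in days per patient**

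| PCT arm t | PCT arm p | A in PCT arm | Written outcome | W in PCT arm | Intended, f = 0 | Intended, f = 1 |
|---|---|---|---|---|---|---|
| 90% | 50% | 3.825 | +0.495 | 2.475 | −0.495 | 0 |
| 87.6% | 50% | 3.723 | +0.393 | 2.409 | −0.561 | −0.168 |
| 80% | 50% | 3.400 | +0.070 | 2.200 | −0.770 | −0.700 |
| 80% | 55% | 3.180 | −0.150 | 2.420 | −0.550 | −0.700 |
| 80% | 60% | 2.960 | −0.370 | 2.640 | −0.330 | −0.700 |

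The first three rows have a 10-point fall in Watch/Reserve starts, and the written outcome has the wrong sign (with equal initiation this holds for any f below 1). In the fourth row the fall is 5 points: the sign is right, but the benefit is understated. In the last row the share is unchanged, so all use falls in proportion and there is no reversal.

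**Step 4: how large a shift reverses the sign**

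Setting t × (7 − 5.5p) equal to the control value 0.9 × (7 − 5.5p₀), where p₀ is the control share, gives

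fall needed = (7 − 5.5p₀)/5.5 × (0.9/t − 1).

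| Control share p₀ | t = 80% | t = 87.6% |
|---|---|---|
| 50% | 4.25/5.5 × 0.125 = 9.7 points | 4.25/5.5 × 0.0274 = 2.1 points |
| 60% | 3.70/5.5 × 0.125 = 8.4 points | 3.70/5.5 × 0.0274 = 1.8 points |
| 70% | 3.15/5.5 × 0.125 = 7.2 points | 3.15/5.5 × 0.0274 = 1.6 points |

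So the larger the fall in initiation, the larger the shift between groups must be before the sign changes.

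**The case against.** The strongest objection is that the protocol nowhere says Access agents are narrow or that broad agents lie in Watch and Reserve. That limit is real: the premise is an assumption until someone opens the linked list. It does not remove the point, because section 5.4 adopts the classification by name and link as its own rule, and the sponsor can check it directly. The rule as written would be right only if Access agents are broad spectrum and agents in the other groups are not.

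A reader might infer that every broad-spectrum day scores zero, that every narrow-spectrum day scores as broad, and that nearly every treated patient is mis-scored. The documents do not support that. If Access holds some broader agents, days on those are scored correctly and the misclassification is partial.

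A reader might also infer that the trial's conclusion on spectrum would be reversed. This too goes beyond the text. The Background says only that narrower prescribing may follow, and reversal needs a shift between groups of sufficient size.

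Finally, the reach is limited. The synopsis lists type of antibiotic as a separate secondary outcome. Days on IV antibiotics and days on any antibiotic do not use the AWaRe group. The outcome plays no part in the co-primary outcomes, the decision table in section 5.3, the sample size or the stopping rules. All of this stands and bears on severity, but it does not make the definition correct.

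**Conclusion.** The definition in section 5.4 is wrong as written, on the assumption, to be confirmed on the linked list, that Access is the mainly narrower-spectrum tier. The outcome then mostly counts the wrong days. It can understate a benefit (−0.15 against −0.55 days per patient at 80% initiation with a 5-point fall in Watch/Reserve starts, taking f = 0) or show it with the opposite sign (+0.07 against −0.77 with a 10-point fall). Those day counts rest on assumed course length, starting shares and de-escalation, and they show the mechanism rather than predict a result. Reversal is a possibility, not an expectation. With a 60% control starting share it needs a fall of more than about 8 points at 80% initiation or about 2 points at 87.6%, and it does not occur under a proportional cut. One secondary outcome is affected, so severity is moderate.

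**What to change.** Check section 5.4 against the linked AWaRe list. Replace the Access group in the definition with the group or groups that count as broad spectrum (expected: Watch or Reserve), and state the version and date of the list used. Apply the same derivation to the Table 3 row in section 17.1 and to the SAP. Report Access-group days separately, as the narrower-spectrum measure if the list confirms that reading.

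The cost is one line in the protocol and a change to the derivation code, made before the outcome is analysed. Antibiotic type and duration are already recorded (Table 1), so no new data are needed. Patient care, the sample size and the co-primary analyses do not change.

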10.1 Adherence

Adherence to the algorithm will be recorded on the CRF and will capture instances where the treating clinician overrules the algorithm if they feel it is appropriate to do so. The ultimate responsibility for clinical care of the patient lies with the treating clinician therefore the cut – off boundaries for initiation times of antibiotics are not mandatory but are recommended guidance to aid clinical decision making. The aim of the trial is to assess whether the use of PCT can improve decision making about which patients receive antibiotics and in what time period. Deviations from the algorithm will not be recorded as protocol violations.

11 Trial procedures

All participants will be prospectively enrolled in the trial from the date of randomisation and will be assessed up to and including day 28 or until they are discharged from clinical care (for those enrolled in the last three months of the trial). Assessments include antibiotic initiation, antibiotic use, adverse events, ICU usage (details of admission to ICU), unscheduled readmissions (ICU re-admissions, re-admissions post discharge), mortality (death for any reason in the 28 days following randomisation), discharge before Day 28, and serious adverse drug reactions (ADRs) to the antibiotic. All clinical management decisions will be recorded at all time points.

At Day 28 and Day 90 there will be a follow-up via telephone or electronically (email/text) about the healthcare utilisation and quality of life of the participant. If unsuccessful a questionnaire booklet will be posted to the participant for them to complete and return with a pre-paid envelope.

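### ICU admission and ICU days are measured over a window that appears to end at index discharge, so a return to ICU after discharge is not an ICU event

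*Protocol*

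**What the plan says.** Protocol section 5.4 lists the outcome as "ICU admission – at any point during admission". Table 3 in section 17.1 turns this into two measures, "People admitted to ICU No of days in ICU", with an in-hospital time frame, analysed by logistic and linear regression respectively.

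Other outcomes are windowed differently. In section 5.4 antibiotic use has two windows: "Number of days on IV antibiotics (during admission and total over the first 28 days". Readmission has its own line, "Readmission to hospital within 90 days", which Table 3 analyses after discharge as "People with one or more readmissions". Mortality is fixed at 28 days (section 5.3) and 90 days (section 5.4).

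On data collection, Table 1 in section 11.1 has a row for ICU usage and a separate row for unscheduled readmissions, which holds "ICU re-admissions, re-admissions post discharge". The text of section 11 lists the same items: "unscheduled readmissions (ICU re-admissions, re-admissions post discharge". Section 11.1 has the research nurse record outcome data daily, "up to and including Day 28, or until discharge".

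**The concern.** A window that ends at discharge ends at an event that occurs after randomisation and may itself depend on the arm. Section 18.2 on health economics counts fewer hospitalisations among the possible savings from the intervention. If PCT-arm patients go home sooner or more often, they have less time in which an ICU admission can be counted. A patient discharged straight from the ED has almost none.

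The safety question for a strategy meant to reduce antibiotic initiation includes the patient who is judged low risk, goes home, deteriorates and comes back to intensive care. Under the stated definition that patient scores no ICU admission and no ICU days. ICU admission is one of the few non-fatal outcomes in the protocol that speak to severity. A comparison that can shrink or change sign because of when patients were discharged would weaken the supporting safety evidence.

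**Working it through.** **Step 1: what window is meant.** The word index appears in neither section 5.4 nor Table 3, so the reading is an inference. Three contrasts in the protocol support it.
- Section 5.4 treats during admission and the first 28 days as two different windows for antibiotic days, and gives ICU admission only the first.
- Table 3 separates the in-hospital time frame (ICU usage) from the after-discharge time frame (readmission).
- Table 1 records ICU usage in one row, and ICU re-admissions and post-discharge readmissions in another.

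No analysis listed in Table 3 counts a post-discharge ICU stay as an ICU event. The readmission analysis scores an ICU return and a ward return alike.

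**Step 2: inputs.** The protocol gives no ICU rate and no figure for this outcome, so there is nothing to reproduce. From section 16.2, the maximum sample is 7676 including 5% dropout, so n = 7676 × 0.95 / 2 = 3,646 per arm. All ICU rates below are assumptions. The tests are simple two-sided 5% comparisons of two proportions, without the site level or the NEWS2 adjustment.

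**Step 3: equal true risk, part of the PCT-arm events moved to after discharge.** Let b be the true risk in both arms and d the differential shift, with no post-discharge events in control.
- Reported OR = [(b − d)/(1 − b + d)] / [b/(1 − b)]
- z = d / √{[b(1 − b) + (b − d)(1 − b + d)]/n}
- Chance of a false significant reduction = Φ(z − 1.96)

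For b = 3% and d = 1 point: z = 0.01 / √[(0.0291 + 0.0196)/3646] = 0.01/0.00365 = 2.74, and Φ(0.78) = 78%.

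| True risk b | Shift d | Share of PCT-arm ICU admissions after discharge (d/b) | z | False reduction |
|---|---|---|---|---|
| 3% | 1 point | 33% | 2.74 | 78% |
| 5% | 1 point | 20% | 2.06 | 54% |
| 10% | 1 point | 10% | 1.46 | 31% |
| 3% | 0.25 point | 8.3% | 0.64 | 9% |
| 5% | 0.25 point | 5% | 0.50 | 7% |
| 10% | 0.25 point | 2.5% | 0.36 | 5% |

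With no shift the chance in this direction is 2.5%. At a 1-point shift the reported ORs are 0.66, 0.79 and 0.89, where the true OR is 1.

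**Step 4: a true harm.** Assume 28-day ICU risks of 6% (control) and 7% (PCT), a true difference of +1.00 point, with 5% of control ICU admissions after discharge. The index-only rate is the true rate × (1 − post-discharge share), so control shows 6 × 0.95 = 5.70%.
- PCT share 5%: 7 × 0.95 = 6.65%, difference +0.95 points.
- PCT share 15%: 7 × 0.85 = 5.95%, difference +0.25 points.
- PCT share 25%: 7 × 0.75 = 5.25%, difference −0.45 points.

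Equal shares leave the comparison almost intact. The distortion comes entirely from a difference in post-discharge share between the arms.

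**The case against.** **The trial's conclusion does not rest on this outcome.** A reader might infer that the non-inferiority safety conclusion is biased. It is not: the decision table in section 5.3 and the rules in sections 16.2 and 17.1 use only IV antibiotic initiation and 28-day mortality, and ICU admission enters no stopping rule. This stands in full.

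**The harm is not invisible.** A reader might also infer that the returning patient disappears from the trial. The patient counts as a readmission within 90 days, and a death counts at 28 and 90 days. ICU re-admissions are recorded, and section 15.5.2 sends hospitalisations and life-threatening events to the IDMC. This stands too. The remaining loss is narrower: no listed comparison shows that the return was to intensive care.

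**The size depends on an unsupported assumption.** The 1-point scenario puts 10% to 33% of PCT-arm ICU admissions after discharge and none in control. Nothing in the protocol supports such a gap, and at 0.25 points the effect is small. The mechanism is also indirect. Section 10 describes a guidance-only algorithm with clinician oversight and senior review, not a discharge rule, and the reduction in hospitalisations is only a possible saving in the economic plan. So a spurious benefit is possible, but the documents do not show it to be likely.

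**The SAP may settle it.** Table 3 is brief, labels antibiotic days in-hospital although section 5.4 also plans a 28-day total, and leaves full details to a SAP that is not shown. That SAP may count ICU stays during readmissions. Even so, the protocol states a window for this outcome, and its natural reading excludes them.

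**Conclusion.** The point holds as a weakness in how a secondary safety outcome is defined. The stated window most naturally ends at index discharge, which the intervention may influence, and no listed analysis counts a later ICU stay as an ICU event. Any bias depends on post-discharge ICU admission differing between arms. With equal shares it is immaterial. With a differential it can understate a harm, and with a large enough one it can reverse the sign.

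The probabilities of a false reduction (78%, 54%, 31% at 1 point; about 9%, 7%, 5% at 0.25 points) rest on assumed risks of 3%, 5% and 10%, no control-arm returns, and 3,646 analysed per arm. They show sensitivity and are not a forecast. The co-primary conclusion is unaffected. The change is worth making because it is cheap and most of the data are already planned.

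**What to change.** In section 5.4 and Table 3, define ICU admission as any ICU admission within 28 days of randomisation, at the index stay or any readmission, and ICU days as the total over the same 28 days. Change the Table 3 time frame for ICU usage to match, carry the definition into the SAP, and keep the index-stay version as descriptive.

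The sources are the ICU re-admission and readmission fields in Table 1 and the day-28 contact in section 11.2, which already asks about readmissions and hospital admissions.

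The cost is more than wording. Post-discharge capture will be less complete than in-stay capture, both for admissions to other hospitals and because section 11.1 allows daily recording to stop at discharge. Section 11 says the same of assessment for patients enrolled in the last three months. Completeness of 28-day ICU status should therefore be reported by arm.
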